## **SUMMARY**

The goal of this prospective, post-market study is to measure AEON™ Endostapler performance for laparoscopic bariatric surgery against the Endo GIA™ Reloads with Tri-Staple™ Technology from Medtronic. Stapler performance will be evaluated primarily by incidence and degree of staple line bleeding from endoscopic images, evaluated by a blinded third-party. The study will include 60 total consecutive cases of individuals undergoing a planned laparoscopic sleeve gastrectomy (LSG). The LSG procedure will be performed according to institutional standard-of-care and all subjects will undergo standard preoperative evaluation as well as post-operative care. Relevant data will be collected using the Data Collection sheet which should be filled out following each procedure by a member of the surgical or nursing team.

**Enrollment:** 60 Subjects Meeting Inclusion/Exclusion Criteria

**Investigator Masking:** None (Open Label)

**Primary Outcome Evaluator Masking:** Yes (Surgeon and Device)

**Devices:** AEON™ Endostapler and Endo GIA™ Reloads with Tri-Staple™ Technology and Ultra Universal Handle

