**Primary Outcome Measure:**

- Incidence of intraoperative staple line bleeding from endoscopic or laparoscopic images as measured by the provided bleeding severity scale

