### **Steps and Procedures:**

The study will include 60 total consecutive cases, randomized for stapler type: 30 with the AEON™ Endostapler and 30 with Endo GIA™ Reloads with Tri-Staple™ Technology. Surgeries will be performed by [name].

All patients will undergo the standard preoperative evaluation pathway. Patients must sign informed consent for the operation.

All firings with the AEON™ Endostapler will be done with THICK MODE for the purposes of this study and shall conform to the AEON™ Instructions for Use. All firings with the Endo GIA™ Reloads with Tri-Staple™ Technology and Ultra Universal Handle should be done according to the Endo GIA™ Instructions for Use.

To measure incidence and degree of staple line bleeding, a third-party blinded evaluator will be used. No sutures, cautery or clips shall be applied during stapling for staple line bleeding, unless required at surgeon's discretion. Following the last firing, a member of the surgical or nursing team or the research coordinator present for the case will count 10 seconds and then capture images with the laparoscope. If bleeding from the staple line requires control prior to the last firing, an additional image should be captured before applying sutures, cautery, clips, etc. Five pictures will be obtained from each case: the pylorus, distal sleeve near the distal end of the staple line, mid-sleeve at the incisura angularis, proximal sleeve and GEJ near the proximal end of the staple line. These photographs will be sent by the research coordinator to the third-party evaluator either electronically or by mail. The third-party evaluator will be blinded to the device of each case. Upon receipt of photographs, the evaluator will evaluate staple line bleeding according to a provided Bleeding Severity Scale for Laparoscope Images (Appendix A) and record results in the Bleeding Severity Evaluation Sheet (Appendix E).

At the end of each case, the surgical team will fill out the relevant sections of the Data Collection Sheet (Appendix C).

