Gastroscopy will be performed, per standard protocol, at the beginning of the case to suction all gastric contents and decompress the stomach as well at the completion of the sleeve gastrectomy. Evaluation for intraluminal bleeding will be performed at the last gastroscopy according to Appendix E. During the last gastroscopy, no suctioning of the gastric contents will be performed until evaluation for bleeding is made and pictures are obtained. The gastroscopy will be performed before any use of clipping at the staple line unless for circumstances judged by the surgeon to be medically necessary to do so before the endoscopy. These instances will also be recorded. Five pictures will be obtained from each case: the pylorus, distal sleeve near the distal end of the staple line, mid-sleeve at the incisura angularis, proximal sleeve and GEJ near the proximal end of the staple line. These photographs will also be sent to the third-party evaluator for evaluation of staple line bleeding according to a provided Bleeding Severity Scale for Endoscope Images (Appendix B). Results will be recorded in the Bleeding Severity Evaluation Sheet (Appendix E).

The determination of laparoscopic and endoscopic staple line bleeding will be based on the picture with the highest bleeding severity score for laparoscopic and endoscopic evaluation separately. Every effort will be made that all pictures prior to any suctioning of the staple line laparoscopically or endoscopically.

All typical post-operative care will continue, including immediate post-operative care prior to hospital discharge as well as the standard post-operative evaluation. A hemoglobin level will be checked at the

recovery room and at 5am on postoperative day #1 per standard protocol. This hemoglobin must be drawn from the upper extremity opposite from the one with the IV running fluids or at the same extremity with the IV running fluids but distal to the IV. For each post-operative period, a member of the surgical or nursing team will fill out the relevant sections of the Data Collection Sheet (Appendix C).

There will be no follow up study data collected after this point, however the patients will continue the standard follow up regimen per the physician's practice.

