**Statistics:**

This is an open-label study (since the patient will be blinded and the evaluation for the primary outcome will be done by a third party blinded to the stapler used). Formal sample size calculations were not performed as the purpose of the study is to demonstrate non-inferiority. The number of subjects was chosen based on feasibility and is considered sufficient to meet the study objectives.

Detailed methodology for summary and statistical analyses of the data collected in this study will be documented in the Clinical Study Report. T-test and chi-square test will be used for univariate analysis of continuous and categorical data respectively. Regression analysis may be used to identify the independent effect of several parameters on primary or secondary outcomes if there are statistically significant differences in univariate analysis.

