## Appendix E – Bleeding Severity Evaluation Sheet

Evaluation Date: \_\_\_\_\_ Evaluator: \_\_\_\_\_

Case #	Staple Line Image from Laparoscope	Staple line bleeding per Bleeding Severity Scale (choose one):				
		No bleeding	Minimal bleeding	Moderate bleeding	Excessive bleeding	Profuse bleeding
	A. Pylorus	1	2	3	4	5
	B. Distal sleeve near distal end	1	2	3	4	5
	C. Distal sleeve	1	2	3	4	5
	D. Proximal sleeve	1	2	3	4	5
	E. GEJ near proximal end	1	2	3	4	5

Case #	Staple Line Image from Endoscope	Staple line bleeding per Bleeding Severity Scale (choose one):				
		No bleeding	Minimal bleeding	Moderate bleeding	Excessive bleeding	Profuse bleeding
	F. Pylorus	1	2	3	4	5
	G. Distal sleeve near distal end	1	2	3	4	5
	H. Distal sleeve	1	2	3	4	5
	I. Proximal sleeve	1	2	3	4	5
	J. GEJ near proximal end	1	2	3	4	5

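### The primary outcome is worded as incidence, with no threshold and no analysis of degree, although the plan says degree is part of the primary evaluation and a 1–5 severity score is recorded

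*Combined protocol and SAP*

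**What the plan says.** The section Primary Outcome Measure has one entry: "Incidence of intraoperative staple line bleeding from endoscopic or laparoscopic images as measured by the provided bleeding severity scale". It states no score at which a patient counts as having bled.

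Two other places describe the primary evaluation more broadly. The Summary says: "Stapler performance will be evaluated primarily by incidence and degree of staple line bleeding from endoscopic images, evaluated by a blinded third-party". Steps and Procedures says: "To measure incidence and degree of staple line bleeding, a third-party blinded evaluator will be used".

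Appendix E scores each of five laparoscopic and five endoscopic pictures from 1 (none) through minimal, moderate and excessive to 5 (profuse). Under Steps and Procedures, the determination for each patient "will be based on the picture with the highest bleeding severity score for laparoscopic and endoscopic evaluation separately".

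Statistics says "T-test and chi-square test will be used for univariate analysis of continuous and categorical data respectively". It does not say which test applies to the primary outcome, names no rank or ordinal method, and leaves detailed methodology to the Clinical Study Report. It gives the purpose as non-inferiority, with no margin and no sample size calculation.

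**The concern.** An incidence is a yes/no event per patient. The only boundary that the scale's labels offer for it lies between grade 1 and grade 2. On that reading a trace of ooze in one picture and profuse bleeding are the same event. Two staplers could bleed equally often but very differently in severity, and the expected difference on the primary outcome would be zero. In a study meant to show that one stapler is not worse, that is the error to guard against.

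A second cost is power. The worst-picture rule pushes patients across the boundary between grades 1 and 2. The more patients cross it, the less a yes/no outcome can separate the arms.

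The choice is also open. The sections disagree on whether degree is primary, and the method is deferred to the report, so it could be settled after the scores are known.

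**Working it through.** **What can be reproduced.** Nothing numerical. The plan gives no expected rate, score distribution, alpha, power or margin. It gives only 60 patients, 30 per arm (Steps and Procedures). Every distribution below is an assumption.

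**1. Effect of the worst-picture rule.** If each picture independently shows grade 2 or higher with probability q, the share of patients at 2 or higher is 1 − (1 − q)^5. For q = 0.1, 0.2 and 0.3 this is 41%, 67% and 83%. Pictures from one patient are correlated, so these are upper values.

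**2. Information kept by incidence.** Under proportional odds, information in grade 1 v 2+ relative to the five-level score is 3p(1 − p)/(1 − Σpᵢ³), where p is the share at grade 1. For an assumed control distribution of 30/40/20/8/2%: 3 × 0.3 × 0.7 / (1 − 0.0995) = 0.63/0.9005 = 0.70. Keeping grades 2–5 in the same proportions and changing only the share at grade 1 gives the values in the table.

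**3. Power, 30 per arm, two-sided 5%, common odds ratio 3 towards worse bleeding.** In the 30% case the odds of grade 1 are 0.3/0.7 = 0.429. Divided by 3 they are 0.143, so 12.5% of the other arm is at grade 1 and incidence is 70% v 87.5%. Check of the 2×2 chi-square by formula:
- Pooled rate 0.7875; null SE = √(2 × 0.7875 × 0.2125/30) = 0.1056.
- Alternative SE = √((0.2100 + 0.1094)/30) = 0.1032.
- Power = Φ((0.175 − 1.96 × 0.1056)/0.1032) = Φ(−0.31) = 38%.

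The power columns come from simulation (200,000 trials per row):

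| Control at grade 1 | Relative information | Incidence chi-square | Five-category chi-square | Rank test | t-test on score |
|---|---|---|---|---|---|
| 80% | 0.99 | 48% | 27% | 49% | 45% |
| 50% | 0.88 | 52% | 39% | 63% | 62% |
| 30% | 0.70 | 38% | 39% | 64% | 63% |
| 15% | 0.44 | 23% | 37% | 62% | 61% |

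With no true difference, the 2×2, rank and t-tests rejected in about 5% of trials and the five-category test in 2.5–4%.

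**4. Equal incidence, different severity.**
- Grades 1–5 at 20/70/10/0/0% v 20/10/30/25/15%: incidence is 80% in both arms, but moderate or worse is 10% v 70%. The incidence test rejects in 5% of trials, its null rate; the rank test in 96%.
- 50/45/5/0/0% v 50/5/15/20/10%: incidence is 50% in both arms, moderate or worse 5% v 45%. The incidence test again rejects in 5%. The rank test reaches only 35%, because half of each arm is tied at grade 1; the t-test reaches 78% and the five-category chi-square over 99%.

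**5. Precision of an ordinal comparison.** For the 30/40/20/8/2% distribution in both arms, the information on the log odds ratio is 30 × 30 × 60/(3 × 61²) × 0.9005 = 4.36. The SE is 1/√4.36 = 0.479, and the 95% limits lie a factor exp(1.96 × 0.479) = 2.6 either side of the estimate.

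**The case against.** The strongest reply is that the plan never says severity will be discarded. No section sets grade 2 or higher as the event, and two sections say that degree is evaluated. This stands: the cut-off is implied by the labels, not stated. The defect is therefore an inconsistent and incomplete definition, which loses severity if the Primary Outcome Measure section is followed as worded.

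A reader might infer that most of the information is thrown away. The documents do not support that. They give no bleeding rate, and the relative information falls below one half only when few patients are free of bleeding (0.44 at 15%). At 80% free of bleeding, almost nothing is lost. Direction matters too: for an odds ratio of 3 towards less bleeding from 30/35/20/10/5%, power is 55% for incidence against 62% for the rank test.

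A reader might also infer that no test named in the plan would use the ordering. That fails as well: a t-test on the 1–5 score uses it and is within a few points of the rank test in the table. The plan simply does not assign it to this outcome. Nor is the rank test best in every case, as the second equal-incidence example shows.

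Finally, the power figures are for two-sided difference tests, while the stated aim is non-inferiority. They compare how sensitive the methods are. A non-significant result from any of them would not show non-inferiority.

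**Conclusion.** The point holds as a gap between sections with a consequence for the analysis. The primary outcome is an incidence without a threshold, degree is named elsewhere as part of the primary evaluation, and no primary analysis of degree is assigned.

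The firmest harm needs no assumption about bleeding rates: an incidence outcome cannot distinguish staplers that differ only in severity among patients who bleed. The power loss is conditional. It runs from about 1 point when 80% of control patients have no bleeding to about 39 points when 15% do, for a common odds ratio of 3 towards worse bleeding and the assumed grade proportions. If the grades are analysed as five unordered categories, power for such a shift is about 37–39% when 15–50% of control patients have no bleeding. Severity is scored for every picture, so nothing is lost at collection and the gap can be closed in the analysis plan.

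**What to change.** In Primary Outcome Measure, define the primary endpoint as the patient's worst 1–5 score for one named modality, with the other modality as supporting. State whether the extra laparoscopic image taken when bleeding needs control before the last firing counts towards the worst score; Appendix E has no row for it. Bring the Summary into line.

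In Statistics, assign an ordinal comparison to this endpoint: a proportional-odds ratio, or the Mann–Whitney effect that accompanies a Wilcoxon test. Judge non-inferiority by its confidence interval against a margin set before data are seen. Report as supporting results the full score distribution by arm and incidence at 2 or higher and at 3 or higher; these show what a single summary can miss.

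The cost is a change of wording. No new data or patients are needed for the change itself. An odds ratio is less familiar to surgeons than a percentage, which the supporting percentages offset. The fix does not make 60 patients precise: with limits a factor of about 2.6 either side of the estimate, setting the margin will show openly what the study can and cannot rule out.

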**Secondary Outcome Measures:**

- Incidence of postoperative leakage requiring intervention through 30-day post-operative evaluation period
- Incidence of intraoperative or postoperative blood transfusion within 72 hours of surgery start time
- Hemoglobin difference between preop hemoglobin and hemoglobin on postoperative day #1 as well as difference between hemoglobin at recovery room and postoperative day #1
- Incidence of reported device-related adverse events through 30-day post-operative evaluation period
- Incidence of product malfunction during stapling
- Total hospitalization time
- Postoperative pain level per standard protocol (0-10 VAS scale completed at Recovery room, 6hrs postop and 7am at POD#1)
- Postoperative nausea presence (0-10 scale VAS completed at Recovery room, 6hrs postop and 7am at POD#1)
- Incidence of vomiting: incidence (at least one per patient) per stapler group, total episodes per group and emesis material (bloody or non-bloody)
- Correlation of number of reloads used and specimen lengths and maximum widths as measured by pathology examination
- Correlation of reload color used with observed bleeding and patient's stomach thickness by path exam
- Correlation of outcome parameters with BMI, visceral fat, gender and age
- Need for clipping the staple line prior to completion of the staple line

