### Intraoperative Outcomes

Product malfunction during stapling? (circle one)	Yes	No
Blood transfusion due to staple line bleeding? (circle one)	Yes	No
Visceral fat:		
Clips required for bleeding (non-routine)? (circle one)	Yes	No

*If yes to any above, please specify:*

Postoperative Outcomes				
	Pre-op	Recovery	6 Hours	POD #1
Pain level per standard protocol (0-10 VAS scale):	N/A			
Nausea level per standard protocol (0-10 VAS scale):	N/A			
Hemoglobin:			N/A	
72 Hours				
Blood transfusion due to staple line bleeding? (circle one)	Yes		No	
30 Days				
Total hospitalization time:				
Number of vomiting episodes:		Bloody	Non-bloody	
Reported device-related adverse events? (circle one)	Yes		No	
Postoperative leakage requiring intervention? (circle one)	Yes		No	

*If yes to any above, please specify:*

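### The preop-to-day-1 hemoglobin drop is understated for any patient transfused before the day-1 draw, and the plan has no rule for such patients

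*Combined protocol and SAP*

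**What the plan says.** Secondary Outcome Measures defines the outcome in two parts. The first is the "Hemoglobin difference between preop hemoglobin and hemoglobin on postoperative day #1"; the second is the corresponding change from the recovery-room value to the day-1 value. Steps and Procedures has hemoglobin checked at the "recovery room and at 5am on postoperative day #1 per standard protocol". It also specifies which arm the sample may come from relative to a running IV, but attaches no condition about earlier transfusion.

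Transfusion is foreseen, because it is a secondary outcome in its own right: "Incidence of intraoperative or postoperative blood transfusion within 72 hours of surgery start time". That window covers all the time from the start of surgery to the 5am draw.

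Appendix C carries the item "Blood transfusion due to staple line bleeding? (circle one") twice, once in the intraoperative block and once at 72 hours. Both are Yes/No and limited by cause. Each block ends with a free-text prompt to explain any Yes. There is no dedicated field for time or units.

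For analysis, the Statistics section says "T-test and chi-square test will be used for univariate analysis of continuous and categorical data respectively". Regression is optional. Beyond that, "Detailed methodology for summary and statistical analyses of the data collected in this study will be documented in the Clinical Study Report". No section says how a transfused patient's day-1 hemoglobin is to be analysed.

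**The concern.** The hemoglobin difference is meant to reflect blood loss. Transfusion is a response to blood loss, and it raises the later of the two values. Followed as written, the plan subtracts a post-transfusion value from the preoperative one, so a patient who bled enough to be transfused can appear to have lost little. The patients affected are likely to be among the heaviest bleeders, who matter most in a comparison of staplers.

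The plan already protects this measurement from one artefact, dilution by running IV fluid, through its rule on the sampling site. Transfusion distorts the same measurement and has no rule.

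At stake is a secondary comparison in a study whose Statistics section gives non-inferiority as its purpose. A distortion that can move the arms towards each other should be dealt with before the data are seen, particularly as the surgeon knows the device used.

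**Working it through.** The plan gives no hemoglobin SD, non-inferiority margin, power calculation or transfusion rate, so there is no figure of its own to reproduce. What follows is an illustration.

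**Inputs from the documents**
- Arm size: "30 with the AEON™ Endostapler and 30 with Endo GIA™ Reloads with Tri-Staple™ Technology", so n = 30 per arm.
- Hemoglobin is scheduled at three times only: preop, recovery room and 5am on day 1.

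**Assumptions (not in the documents)**
- Rise per unit: 0.5 to 1.5 g/dL. Two units per transfused patient gives a rise r = 1 to 3 g/dL.
- SD of the hemoglobin difference: 1.0 g/dL, with 0.8 and 1.5 as alternatives.
- Transfusion rate: 1% to 10%.

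**Step 1. Shift in one arm's mean drop.** With k patients transfused before the draw, shift = k × r / 30.
- k = 1: 1 × 1 / 30 = 0.03 to 1 × 3 / 30 = 0.10 g/dL.
- k = 3: 3 × 1 / 30 = 0.10 to 3 × 3 / 30 = 0.30 g/dL.

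**Step 2. Shift against sampling error.** SE of the difference between arms = SD × √(2/30), which is 0.207, 0.258 and 0.387 g/dL at SD 0.8, 1.0 and 1.5. At SD 1.0:
- k = 1: 0.033/0.258 = 0.13 to 0.10/0.258 = 0.39 SE.
- k = 3: 0.10/0.258 = 0.39 to 0.30/0.258 = 1.16 SE.

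**Step 3. Direction between arms.** The comparison moves by (sum of rises in AEON − sum of rises in Endo GIA) / 30.
- More early transfusions in AEON: its mean drop shrinks and AEON looks better than it is.
- More in Endo GIA: AEON looks relatively worse.
- Similar numbers and rises in both: the shifts roughly cancel.

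**Step 4. Worked example.** Suppose 3 of 30 patients in one arm truly drop 4 g/dL and everyone else in either arm drops 1 g/dL. The true means are (3 × 4 + 27 × 1)/30 = 1.30 and 1.00, a difference of 0.30 g/dL. If the three are transfused before the draw, the recorded difference is 0.20, 0.10 or 0.00 g/dL at r = 1, 2 or 3.

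**Step 5. Chance that it arises.** P(at least one of 60 transfused) = 1 − (1 − p)^60, which is 0.45, 0.70, 0.95 and 0.998 at p = 1%, 2%, 5% and 10%. This counts any transfusion; only those before the 5am draw matter here.

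**Step 6. The second difference.** An intraoperative transfusion raises both the recovery and the day-1 values, so much of it cancels. The recovery-to-day-1 difference is distorted mainly by transfusions between those two draws.

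**Step 7. Carrying a pre-transfusion value forward.** For an intraoperative transfusion, the last scheduled earlier value is the preop value, so the drop becomes preop − preop = 0. In the Step 4 example with r = 2, a patient with a true drop of 4 has a raw recorded drop of 4 − 2 = 2; substitution would make it 0. For a transfusion after the recovery draw, the recovery-to-day-1 difference becomes recovery − recovery = 0.

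**The case against.** The strongest case against is that the consequence is small. This is one of 13 secondary outcome bullets, and the primary outcome is scored from images. Patients with bleeding disorders are excluded. Transfusion incidence is reported separately, so a reader would see the event beside the hemoglobin result. Every figure above rests on assumed inputs, and 0.30 g/dL requires three patients in one arm, each given 2 units with the largest assumed rise per unit, and none in the other arm. All of that stands and sets the level of the point. It does not remove it: separate reporting shows that a transfusion occurred but leaves the hemoglobin comparison distorted.

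The gap can also be seen as one instance of deferring analysis detail to the Clinical Study Report. That is partly so. But the outcome as defined already yields a value for a transfused patient, and that value is biased, so the problem goes beyond missing detail.

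Two stronger readings are tempting, and the documents do not support either.
- A reader might infer that the bias always favours non-inferiority. Only the shift within a transfused patient is one-way. The effect on the comparison depends on which arm has more early transfusions (Step 3), and the plan sets no non-inferiority margin for hemoglobin.
- A reader might infer that the information is lost for good. Appendix C has a separate intraoperative row, which by itself places a transfusion before the day-1 draw. It also has free text where time and units could be written, and the protocol provides for access to source documents. What is uncertain is the timing of a postoperative transfusion relative to 5am, which the sheet does not reliably capture.

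**Conclusion.** The point holds as a minor one. Followed as written, the plan understates the preop-to-day-1 drop of any patient transfused before the 5am draw. This pulls the arms together if the worse stapler causes more such transfusions, and it favours non-inferiority only if AEON has more of them. The recovery-to-day-1 difference is affected mainly by transfusions between its two draws.

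The size is about 0.03 to 0.10 g/dL on an arm mean for one patient given 2 units, assuming 0.5 to 1.5 g/dL per unit, or 0.13 to 0.39 SE at an assumed SD of 1.0 g/dL. Three such patients in one arm and none in the other would give 0.10 to 0.30 g/dL. With no early transfusions the effect is nil. That the bias exists follows from the outcome definition and the draw time; its size rests wholly on the assumptions.

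**What to change.** Keep the t-test on raw differences and prespecify one sensitivity analysis beside it: a Wilcoxon rank-sum comparison of the hemoglobin drop in which every patient transfused before the day-1 draw receives the worst rank. Do not substitute the last scheduled pre-transfusion value, which can force a zero drop in a serious bleeder (Step 7).

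Add date/time and units to the transfusion rows of Appendix C. Because those rows ask only about transfusion for staple line bleeding while the transfusion outcome is not limited by cause, the fields should be completed for every transfusion.

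The cost is one sentence of analysis plan and two fields completed only for transfused patients. The drawback is that the rank result is not expressed in g/dL, so it supplements the mean difference and does not replace it. Nothing in patient care or blood sampling changes.

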## Appendix C – Data Collection Sheet

Surgery Date: \_\_\_\_\_ Surgeon: \_\_\_\_\_ Hospital: \_\_\_\_\_

Stapler Type (Circle): AEON™ Endostapler Endo GIA™ with Tri-Staple™ Technology

Patient Gender: \_\_\_\_\_ Patient Age: \_\_\_\_\_ Patient BMI: \_\_\_\_\_

AEON™ Endostapler	Black 60mm	Purple 60mm	Purple 45mm	Orange 60mm	Orange 45mm	White 60mm	White 45mm
Quantity Reloads Used							

Endo GIA™ with Tri-Staple™ Technology	Black 60mm	Black 45mm	Purple 60mm	Purple 45mm	Tan 60mm	Tan 45mm
Quantity Reloads Used						

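### The adverse-event outcome counts only events reported as device-related on an unmasked form; all and serious events should also be compared by arm

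*Combined protocol and SAP*

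**What the plan says.** Secondary Outcome Measures lists "Incidence of reported device-related adverse events through 30-day post-operative evaluation period" as one of thirteen secondary outcomes. On Appendix C, the only general adverse-event item is a yes/no row in the 30-day block, "Reported device-related adverse events? (circle one", with free text if the answer is yes. An event judged unrelated to the device has no row of its own on that sheet.

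On who completes it, Steps and Procedures says that for each post-operative period "a member of the surgical or nursing team will fill out the relevant sections of the Data Collection Sheet". The same sheet opens with "Stapler Type (Circle): AEON™ Endostapler Endo GIA™ with Tri-Staple™ Technology". The Summary gives investigator masking as "None (Open Label".

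Masked review is described for the bleeding images: "To measure incidence and degree of staple line bleeding, a third-party blinded evaluator will be used". The Statistics section relies on masking of the patient and of that evaluator: "since the patient will be blinded and the evaluation for the primary outcome will be done by a third party blinded". The available text gives no criteria for device-relatedness and no masked adjudication of it.

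**The concern.** In a randomised trial, adverse events can be compared between arms without anyone deciding what caused them. This outcome puts a causality judgement ahead of the comparison, and the people completing the form can see which stapler was used. If the same event is more readily blamed on one stapler than on the other, the comparison reflects that habit as well as the devices.

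The Statistics section gives non-inferiority as the purpose. Under-attribution in the worse arm would push the result towards no difference, which is the convenient direction here. Over-attribution to an unfamiliar or disfavoured device would do the reverse. At stake is whether the adverse-event comparison can be read at face value.

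**Working it through.** **The documents side by side.** The outcome definition and the form row agree: both admit only device-related events. The form is completed by staff, the stapler is circled on it, and investigators are unmasked. The masked evaluator's task is confined to images. So nothing in the available text shields the relatedness judgement from knowledge of the arm.

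**Inputs.** Arm sizes are from Steps and Procedures: "30 with the AEON™ Endostapler and 30 with Endo GIA™ Reloads with Tri-Staple™ Technology". The chi-square test for categorical data is from Statistics. The plan states no significance level, event rate or attribution rate, so two-sided 0.05 and every rate below are assumptions. The plan has no figure of its own to reproduce, because it says that no sample-size calculation was done.

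**Formula.** Let p1 and p2 be the proportions of patients with any adverse event in the two arms (either stapler may be arm 1). Let q1 and q2 be the probabilities that such a patient's event is reported as device-related. The recorded proportion in each arm is p × q, so

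recorded risk ratio = (p1/p2) × (q1/q2).

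**Results at 30 per arm.** The last column is the chance of p < 0.05 from exact enumeration of the uncorrected chi-square test.

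| Any event | Called device-related | Recorded | Difference (points) | Ratio | Chance of p < 0.05 |
|---|---|---|---|---|---|
| 30% vs 10% | all events counted | 30% vs 10% | 20 | 3.0 | 50% |
| 30% vs 10% | 50% vs 50% | 15% vs 5% | 10 | 3.0 | 26% |
| 30% vs 10% | 50% vs 80% | 15% vs 8% | 7 | 1.9 | 14% |
| 30% vs 10% | 25% vs 75% | 7.5% vs 7.5% | 0 | 1.0 | 5% |
| 20% vs 10% | all events counted | 20% vs 10% | 10 | 2.0 | 19% |
| 20% vs 10% | 40% vs 80% | 8% vs 8% | 0 | 1.0 | 5% |
| 20% vs 20% | 50% vs 80% | 10% vs 16% | −6 | 0.63 | not calculated |

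Three things follow.

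- Attribution that is equal in both arms keeps the ratio but shrinks the absolute difference.
- Unequal attribution can erase a real difference (fourth and sixth rows) or create one where none exists (last row). The direction is not fixed.
- Counting all events removes the filter but does not make the comparison well powered: about 50% for 30% vs 10%, and about 19% for 20% vs 10%.

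**In whole patients.** Suppose 6/30 vs 3/30 have any event, and 2 of the 6 and 2 of the 3 are called device-related. The outcome then reads 2/30 vs 2/30, and a 10-point difference becomes 0. The all-event counts would not be significant either: chi-square = 60 × (6×27 − 3×24)² / (30 × 30 × 9 × 51) = 486,000 / 413,100 = 1.18, p about 0.28. What is lost is an estimate free of the filter, not a significant finding.

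**The case against.** The case against giving this much weight is substantial, and most of it stands.

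- **Other outcomes cover the main harms.** A reader might infer that safety is compared only through device-attributed events. It is not. Secondary Outcome Measures also lists leakage requiring intervention, transfusion within 72 hours, hemoglobin change, product malfunction and vomiting, none defined by device-relatedness, and the primary bleeding outcome has a masked evaluator. The cover is incomplete: transfusion stops at 72 hours, hemoglobin at the first postoperative day, and leakage counts only if it requires intervention. Appendix C also narrows transfusion to that caused by staple line bleeding, which the outcome definition does not.
- **Wider collection cannot be ruled out.** A reader might infer that unrelated events go unrecorded. Text between Steps and Procedures and Termination of the Study was not available for review and may deal with event reporting. Withdrawal of Subjects requires follow-up of ongoing adverse events with no device limit. The point therefore rests only on the outcome definition and the form row.
- **Who judges relatedness is partly inferred.** The plan says who fills in the sheet, not who decides cause, and it does not state the masking of ward nurses. With the stapler printed on the sheet, unmasked judgement is the natural reading, but it is not stated.
- **Unequal attribution is not always bias.** If one stapler truly causes more events, a correct judgement would also attribute a larger share in that arm, and the filter would then sharpen the contrast. All-event counts include events due to the sleeve procedure itself, which can dilute a difference. This is a good reason to keep the device-related table, not to rely on it alone.
- **An all-event comparison is not automatically unbiased.** Unmasked staff still decide what to record. Withdrawn subjects are replaced, and major deviations may lead to exclusion case by case. Either can disturb the randomised comparison whatever is done about attribution.

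**Conclusion.** The concern holds in a limited form. This one secondary outcome, as defined, depends on a causality judgement that the available text does not protect from knowledge of the stapler, and its between-arm comparison can be biased in either direction. The size is unknown; the table shows what assumed rates would produce, not what is expected.

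The documents do not support a claim that attribution will differ by arm, or that any bias must favour no difference. The conclusion assumes that those completing the sheet, or informing it, know the stapler and influence the relatedness call. The outcome is secondary and several attribution-free outcomes sit beside it, so this is a cheap improvement and not a threat to the trial's main result.

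**What to change.** Replace the 30-day adverse-event row on Appendix C with one that asks whether any adverse event occurred through 30 days, with a description, and with seriousness and device-relatedness as sub-items. Amend the outcome in Secondary Outcome Measures to match. Report all adverse events and serious adverse events by randomised arm regardless of attribution, with the device-related subset alongside, and give confidence intervals for the differences.

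The cost is one form row, one amended outcome line, a short table and slightly more recording up to the one-month visit. If all events are already collected, only the analysis changes. Three limits remain: procedure-related events may dilute the all-event comparison (hence both tables), precision at 30 per arm is low, and event recording is still unmasked.
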